2. The trial will be conducted in accordance with International Council on Harmonisation Good Clinical Practice (ICH GCP), applicable United States (US) Code of Federal Regulations (CFR), and the [specify NIH Institute or Center (IC) [Terms and Conditions of Award. The Principal Investigator will assure that no deviation from, or changes to the protocol will take place without prior agreement from the funding agency and documented approval from the Institutional Review Board (IRB), and the Investigational New Drug (IND) or Investigational Device Exemption (IDE) sponsor, if applicable, except where necessary to eliminate an immediate hazard(s) to the trial participants. All personnel involved in the conduct of this study have completed Human Subjects Protection and ICH GCP Training.

For either option above, the following paragraph would be included:

The protocol, informed consent form(s), recruitment materials, and all participant materials will be submitted to the IRB for review and approval. Approval of both the protocol and the consent form(s) must be obtained before any participant is consented. Any amendment to the protocol will require review and approval by the IRB before the changes are implemented to the study. All changes to the consent form(s) will be IRB approved; a determination will be made regarding whether a new consent needs to be obtained from participants who provided consent, using a previously approved consent form.

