4 STUDY DESIGN

4.1 OVERALL DESIGN

A two-group, single-blinded (raters are not part of intervention) and randomized clinical trial (RCT) with stratification for traumatic or non-traumatic injury will be performed. The stratification will help to ensure balanced groups prior to randomization.

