9 STATISTICAL CONSIDERATIONS

9.1 SAMPLE SIZE DETERMINATION

All statistical tests will be 2-sided. The outcome measures will be tested at a 0.05 level of significance. SPSS will be used to conduct the statistical analyses. All participants who have EAW sessions will be included (regardless of the number of sessions they complete before discharge, but the number and reason of missing EAW sessions will be recorded). To test the three main hypotheses of the proposed study, the change score of each outcome between baseline and discharge will be calculated. The change score will be compared between the intervention and control groups using independent t-test analyses (if the outcomes are not normally distributed, Mann-Whitney tests will be used).

Since the primary aim of the study is to compare the improvement of FIM scores between the groups, the FIM score results from the preliminary data were used to perform the power analysis for this study. In the preliminary data, the mean change in FIM score from the intervention group was 35 ± 12 , and the control group was 22 ± 13 . The effect size of the FIM score change in our preliminary data was 1.07 (controlling for the different number of participants between the two groups). The power analysis showed that using the effect size (1.07) and 0.05 level of significance with two-sided analysis in independent t-test, a total of 30 participants will provide the study 80% power.

To account for an expected attrition rate of about 25%, 40 participants will be enrolled. It is expected that 30 participants will complete the study (the reasons and number of screening failures and dropouts will be recorded).

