9.2 STATISTICAL ANALYSES

9.2.1 GENERAL APPROACH

All statistical tests will be 2-sided. The outcome measures will be tested at a 0.05 level of significance. SPSS will be used to conduct the statistical analyses. All participants who have EAW sessions will be included (regardless of the number of sessions they complete before discharge, but the number and reason of missing EAW sessions will be recorded). To test the three main hypotheses of the proposed study, the change score of each outcome between baseline and discharge will be calculated. The change score will be compared between the intervention and control groups using independent t-test analyses (if the outcomes are not normally distributed, Mann-Whitney tests will be used).

In addition to the primary analysis, several secondary analyses will be performed. 1) Each of the outcomes will be compared between pre- and post-EAW training using a paired t-test analysis (if the outcomes are not normally distributed, Wilcoxon signed-rank test will be used). 2) Analyses will be performed to determine the relationships between the change of outcome measures and EAW training time (including sessions, up time, walking time, or total number of steps per session and across all sessions) using correlation coefficients, regression analyses (stepwise and logistic), analyses of covariance, and nonparametric analyses as appropriate. 3) An additional exploratory post

hoc analyses will be to determine the relationship of participant's baseline characteristics with successful use of the exoskeleton. This post hoc analysis would serve as pilot data to begin to determine who is a good candidate for EAW training during AIR for a future study.

References:

1. Simpson, L.A., et al., *The health and life priorities of individuals with spinal cord injury: a systematic review*. J Neurotrauma, 2012. **29**(8): p. 1548-55.
2. Ditunno, P.L., et al., *Who wants to walk? Preferences for recovery after SCI: a longitudinal and cross-sectional study*. Spinal Cord, 2008. **46**(7): p. 500-6.
3. Tate, D.G., C.Z. Kalpakjian, and M.B. Forchheimer, *Quality of life issues in individuals with spinal cord injury*. Arch Phys Med Rehabil, 2002. **83**(12 Suppl 2): p. S18-25.
4. [name], T.N. and K.T. Ragnarsson, *Pain after spinal cord injury*. Phys Med Rehabil Clin N Am, 2000. **11**(1): p. 157-68.

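### The between-group test is an unadjusted t-test on change scores: valid in form, but it ignores the stratification factor and fixes the baseline slope at 1, so precision and protection against chance imbalance may be lost

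*Combined protocol and SAP*

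**What the plan says.** Sections 9.1 and 9.2.1 give the same rule. For every outcome, "the change score of each outcome between baseline and discharge will be calculated", and then "The change score will be compared between the intervention and control groups using independent t-test analyses". The fallback is also unadjusted: "if the outcomes are not normally distributed, Mann-Whitney tests will be used".

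Section 4.1 describes a randomised trial "with stratification for traumatic or non-traumatic injury will be performed" and gives the reason: "The stratification will help to ensure balanced groups prior to randomization". Section 9 does not mention the factor again.

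Covariance analysis appears once, in the second of the secondary analyses in section 9.2.1: "analyses of covariance, and nonparametric analyses as appropriate". That item relates outcome change to the amount of exoskeleton training. Controls receive none, so it cannot serve as an adjusted comparison of the arms.

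The sample size in section 9.1 rests on the same unadjusted test: "The effect size of the FIM score change in our preliminary data was 1.07", from mean FIM changes of 35 and 22, with a claimed 80% power from 30 participants.

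**The concern.** A change score uses the baseline value only by subtracting it, which amounts to a regression of discharge on baseline with the slope set at 1. If the true slope is below 1, two things follow. The comparison is noisier than it needs to be, and part of any chance baseline difference between the arms passes into the estimated effect. In a trial of 20 against 10 completers, such differences are common.

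The stratification factor raises a second issue. Stratifying balances it across the arms, but a test that omits it leaves its between-patient variation in the error term. If injury type is prognostic, the test becomes conservative and part of the benefit of stratifying is lost.

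The plan also has no prespecified adjusted estimate. If the arms turn out unequal at admission, any adjustment chosen at that point is open to the charge that it was driven by the data.

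**Working it through.** **Inputs from the documents.** Effect size d = 1.07 on FIM change; expected difference 35 − 22 = 13 points; two-sided alpha 0.05; 30 completers split 20:10 (sections 6.1.1, 6.2 and 9.1).

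**Inputs that had to be assumed.** The documents give no baseline-discharge correlation (rho), no admission or discharge SDs, no stratum proportions and no stratum effect. I take rho from 0.3 to 0.9, a discharge-to-baseline SD ratio k of 1 to 1.4, strata split 50:50 and balanced within arm, and a stratum effect of 0, 0.5 or 0.8 change-score SD.

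**The plan's own figure.** The noncentrality is 1.07 × √(20 × 10/30) = 2.763. With 28 df the critical value is 2.048, and the power is 76.0%. The stated 80% is roughly matched by the normal approximation at 20:10 (78.9%) or by an exact t-test at 15:15 (80.7%). The reference for what follows is therefore 76%.

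**Power with adjustment.** With equal SDs, the variance of the adjusted estimate relative to the change score is (1 + rho)/2 before small-sample cost: 0.65, 0.75, 0.85 and 0.95 at rho 0.3, 0.5, 0.7 and 0.9. The table comes from simulation (60,000 trials per case) of discharge score on group, baseline and stratum with 26 residual df. The slope is k × rho, and each cell gives unadjusted / adjusted power.

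| k | rho | Slope | No stratum effect | Stratum effect 0.5 SD |
|---|---|---|---|---|
| 1 | 0.3 | 0.30 | 76% / 90% | 77% / 92% |
| 1 | 0.5 | 0.50 | 76% / 85% | 77% / 88% |
| 1 | 0.7 | 0.70 | 76% / 81% | 76% / 83% |
| 1 | 0.9 | 0.90 | 76% / 76% | 77% / 79% |
| 1.2 | 0.8 | 0.96 | 76% / 74% | 76% / 77% |
| 1.4 | 0.7 | 0.98 | 76% / 74–75% | 77% / 77% |

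The gain is up to about 14 points without a stratum effect. It vanishes, or becomes a loss of up to about 2 points, when the slope is near 1 and the stratum is not prognostic.

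**Type I error** (k = 1, rho 0.5, strata exactly balanced among completers). The unadjusted t-test gives about 5.0%, 4.3% and 3.1% at stratum effects of 0, 0.5 and 0.8 SD. Repeat simulations put the last figure between 3.1% and 3.6%. The adjusted model stays at about 5%.

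**Chance imbalance.** The standard error of the baseline difference is √(1/20 + 1/10) = 0.387 SD. The probability of a difference above 0.5 SD in either direction is 2 × [1 − Φ(0.5/0.387)] = 0.197.

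**Effect of a 0.5 SD imbalance on the FIM estimate** (equal SDs). The change SD is 13/1.07 = 12.15, the baseline SD is 12.15/√(2(1 − rho)), and the shift is (1 − rho) × 0.5 × baseline SD.

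| rho | Baseline SD | Shift (FIM points) | Share of the expected 13 |
|---|---|---|---|
| 0.3 | 10.3 | 3.6 | 28% |
| 0.5 | 12.1 | 3.0 | 23% |
| 0.7 | 15.7 | 2.4 | 18% |
| 0.9 | 27.2 | 1.4 | 10% |

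**The case against.** The best defence is that nothing here is an error. The t-test on change matches the hypothesis, which is worded in terms of change, and the power calculation. In form it is unbiased over randomisation and holds its level. That is correct. Adjustment estimates the same treatment effect, however, so the match shows the plan to be coherent without showing it to be better.

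The benefit also rests on figures the documents do not give, and the larger gains need equal admission and discharge SDs. This stands: no gain, or a small loss, cannot be excluded. The loss is about 2 points in the cases examined.

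The type I figures assume exact balance of 50:50 strata among completers, whereas section 9.1 expects about 25% attrition. With balance at enrolment and random dropout to 20:10, the error is 4.4% and 4.1% at stratum effects of 0.5 and 0.8 SD. With exactly balanced 20:80 strata it is 4.5% and 3.7%. The direction holds, but 3.1% is near the extreme.

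The word valid must also be limited to the form of the test. It presumes that all randomised participants are analysed or that dropout is uninformative; who enters the analysis is a separate question.

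Finally, an adjusted model could be added as a supporting analysis only. That would supply the missing adjusted estimate but would not recover power in the primary test.

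**Conclusion.** The concern holds as an improvement the plan should make; it does not invalidate the analysis. The between-group comparison uses neither the stratification factor nor a fitted baseline slope, and nothing else in the document supplies an adjusted comparison.

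The size is known only as a range. Against 76% for the planned test, adjusted power runs from about 74% (slope near 1, stratum not prognostic) to about 90% (rho 0.3, equal SDs), and slightly higher with a prognostic stratum. The chance of a baseline difference above 0.5 SD, about one in five, depends only on the 20:10 split and approximate normality. Its effect on the estimate depends on the assumed rho and SDs. The power and FIM figures concern FIM alone; the other outcomes would have their own correlations. Confidence in the size of the gain is moderate.

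**What to change.** Prespecify as the primary between-group analysis a linear model of the discharge score (or, equivalently for the group effect, the change) on group, baseline value of the same outcome and traumatic/non-traumatic stratum. Report the adjusted difference with its 95% confidence interval.

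For outcomes expected to be clearly non-normal, such as CRP, name in advance for each outcome the transformation or the rank-based version of the same adjusted model. This keeps the plan's provision for non-normal data without leaving the choice until the data are seen. Keep the planned t-test and Mann-Whitney test as sensitivity analyses.

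The cost is small. Baseline values are already needed for the change scores, injury type must be known in order to stratify, and SPSS fits the model. It uses two further degrees of freedom and could lose up to about 2 points of power in the unfavourable case. Section 9 is protocol text, so the compliance statement applies: "Any amendment to the protocol will require review and approval by the IRB before the changes are implemented to the study".

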3 OBJECTIVES AND ENDPOINTS

OBJECTIVES	ENDPOINTS
Primary	
To determine the effects of AIR with EAW compared with AIR without EAW (same total therapy time) on the changes from admission to discharge in the International Standards for Neurological Classification of Spinal Cord Injury (ISNCSCI) upper and lower extremity motor scores, Functional Independence Measure (FIM) scores, and Spinal Cord Independence Measure (SCIM) scores as classified by clinicians.	ISNCSCI examination results FIM scores SCIM scores
Secondary	
To determine the effects of AIR with EAW compared to AIR without EAW on reducing pain using the International Spinal Cord Injury Basic Pain Data Set 2.0 (ISCIBPDS 2.0) measures where type of pain is classified with the Spinal Cord Injury Pain Instrument (SCIPI).	Intensity of pain
Tertiary/Exploratory	
To determine the effects of AIR with EAW compared with AIR without EAW on reducing a specific systemic inflammatory mediator (C reactive protein, CRP).	CRP results

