6 STUDY INTERVENTION

6.1 STUDY INTERVENTION(S) ADMINISTRATION

6.1.1 STUDY INTERVENTION DESCRIPTION

Intervention (N=20): In the intervention group, participants will receive locomotor training provided with an Ekso™ powered exoskeleton according to the standard of care of AIR at Mount Sinai Hospital with the exception that the EAW training will be incorporated into the designated therapy times (3 hours of physical therapy (PT) and/or occupational therapy (OT)) which will be provided as determined by the clinical team from the earliest time they are identified to be able to safely stand, through discharge. The goal of EAW intervention is to complete three or more sessions of EAW training a week during the AIR period (after enrolling into the study until discharge). One EAW session is defined to have at least 20 minutes of uptime in the device (based on data output from EksoTM, device, not including donning and doffing time). EAW sessions will include device fitting, instruction for sit-to-stand and stand-to-sit maneuvers; balance and fall protection training; and walking on smooth indoor surfaces with total or variable device assistance. The clinical team will determine the frequency, duration, and intensity of each EAW session based on the participant's response to the previous session.

Control (N=10): In the control group, participants will receive standard of care AIR which includes three hours of PT and/or OT per day until they are discharged. This standard of care AIR may include bed mobility, balance, strength, gait, transfers, and wheelchair mobility training to improve participants' independence in activities of daily living, such as bathing, eating, dressing, grooming, and wheelchair use but does not include EAW. The two groups (control and intervention) will have the same total amount of therapy time.

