6.2 MEASURES TO MINIMIZE BIAS: RANDOMIZATION AND BLINDING

Eligible participants will be randomized into either the intervention group or the control group. In order to provide more opportunities for participants to accept EAW training, the intervention group will have 20 participants, and the control group will have 10 participants.

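### Stepwise selection among overlapping EAW exposure measures yields p-values that ignore the selection; one pre-specified exposure and one linear model would serve this secondary analysis better

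*Combined protocol and SAP*

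**What the plan says.** Section 9.2.1 (General Approach) lists three secondary analyses after the between-group comparison. The second examines "the relationships between the change of outcome measures and EAW training time". Training time is described as "including sessions, up time, walking time, or total number of steps per session and across all sessions". The methods offered are correlation coefficients, "regression analyses (stepwise and logistic" models, analysis of covariance and nonparametric methods, and the choice among them is left to what turns out to be suitable.

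Outcomes enter as differences: "the change score of each outcome between baseline and discharge will be calculated". Section 3 lists the primary outcomes as "ISNCSCI examination results FIM scores SCIM scores", the secondary as "Intensity of pain" and the tertiary as C-reactive protein (CRP).

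Only the EAW arm has exposure data. Section 6.1.1 gives its size as "Intervention (N=20", and section 6.2 agrees: "the intervention group will have 20 participants, and the control group will have 10 participants".

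The plan names no main exposure measure, no criterion for entering or removing a variable, no covariates and no multiplicity control for this analysis. A general two-sided 0.05 level applies.

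**The concern.** Stepwise regression picks the candidate most strongly related to the outcome in the sample and then reports its p-value as if it had been the only candidate. With several candidates and several outcomes, the chance that something enters when nothing is related is well above 5%.

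The exposures also overlap by construction, because a total is the number of sessions multiplied by the per-session mean. Which of them is selected is therefore likely to change from sample to sample. A reader could conclude that, say, steps matter and up time does not, when the data cannot separate the two.

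Exposure is not assigned either. The synopsis says that participation lasts as long as the inpatient stay, and section 6.1.1 lets the clinical team set the frequency, duration and intensity of sessions from the participant's earlier response. Totals therefore partly reflect length of stay and tolerance, which stepwise selection does nothing to address.

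At stake is the credibility of any statement about which aspect of training goes with recovery.

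**Working it through.** The plan states no error rate or precision for this analysis, so there is no figure of its own to reproduce.

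**Inputs from the documents**
- EAW participants: 20 (sections 6.1.1 and 6.2).
- Level: 0.05, two-sided (section 9.2.1).
- Candidate exposures: four named (sessions, up time, walking time, steps). On the broad reading there are seven: sessions, plus three measures each taken per session and in total (1 + 3 × 2 = 7).
- Outcomes: six, counting upper and lower motor scores, FIM, the Spinal Cord Independence Measure (SCIM), pain intensity and CRP.

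**Assumptions**
- Entry threshold of 0.05, since none is given.
- Common correlation among exposures from 0 to 0.95.
- Correlation among outcomes from 0 to 0.7.
- n varied from 15 to 27. The upper value is two thirds of the 40 to be enrolled: 40 × 2/3 = 26.7.

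**Step 1. Limit for independent exposures.** The chance that at least one of k enters is 1 − 0.95^k.
- k = 4: 1 − 0.95^4 = 18.5%.
- k = 7: 1 − 0.95^7 = 30.2%.

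**Step 2. Correlated exposures.** Simulation with no true association, n = 20 and 20,000 replicates. The event is that the largest absolute correlation passes the entry threshold, which is the first step of forward selection.

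| Correlation among exposures | 0 | 0.3 | 0.5 | 0.7 | 0.8 | 0.9 | 0.95 |
|---|---|---|---|---|---|---|---|
| 4 candidates | 18.3% | 17.7% | 15.7% | 13.5% | 11.7% | 9.3% | 8.5% |
| 7 candidates | 30.0% | 27.1% | 23.7% | 18.8% | 15.4% | 12.0% | 9.3% |

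The independent column agrees with step 1. At n = 15 the ranges are 8.0% to 18.4% and 9.8% to 30.6%. At n = 27 they are 8.0% to 18.7% and 9.3% to 29.6%. Sample size therefore hardly matters to this rate.

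**Step 3. Totals built as products.** Seven exposures were simulated with totals equal to sessions times per-session means, giving average pairwise correlations of 0.46 to 0.56. At least one entered in 14% to 20% of runs per outcome. Across all six outcomes, at least one false entry occurred in 41% to 74% of runs. The low end has the more tightly linked exposures and outcomes correlated at 0.7; the high end has the looser exposures and independent outcomes.

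**Step 4. What a selected predictor must look like.** With n = 20 the critical t on 18 degrees of freedom is 2.101. The critical correlation is 2.101 / √(18 + 2.101²) = 2.101 / 4.734 = 0.444. Any first predictor that enters therefore appears to explain at least 0.444² = 20% of the variance, even if the truth is zero.

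**Step 5. One pre-specified exposure.** The false-positive chance returns to 5% per outcome. With no covariates, 80% power at n = 20 needs a true correlation of about tanh[(1.960 + 0.842) / √17] = tanh(0.680) = 0.59. Only strong associations can be detected, whatever method is chosen.

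**The case against.** The strongest reply is that the sentence is a menu. The methods are to be used where suitable, the exposures are joined by *or*, and nothing says that all of them go into one stepwise model for every outcome. That is fair, and it is why the result is a range. It does not remove the point: stepwise regression is named, and no rule says when it would be used or on which candidates.

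Several stronger readings might be inferred, and the documents do not support them.

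- **That there are at least seven candidates.** Four are named. The phrase about per session and across all sessions may qualify steps alone, so seven is the broad reading and not a minimum.
- **That overlap and small n cause the false selections.** Overlap lowers the rate and n barely moves it. The number of candidates and outcomes drives it. Overlap and small n instead make the selected measure unstable and its estimate exaggerated.
- **That logistic regression has nothing binary to model.** Section 8.1 records the type of pain, the completeness of injury at admission and discharge, and walking tests given only to those who can walk independently. Any of these could be made a binary outcome without cutting a score. What the plan lacks is the name of the outcome, which is missing detail and would not carry a point by itself.
- **That the results are to serve as pilot data.** That remark belongs to the third analysis, on baseline characteristics and successful device use.

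It is also true that the error rate in the working is ordinary multiplicity. Unadjusted correlations for the same exposures would cross the 5% line about as often. The difference is that they would all be shown, with none presented as the winner.

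**Conclusion.** The point holds as a modest improvement to a secondary analysis. With no true association, stepwise selection at n = 20 lets in at least one exposure in 8.5% to 18% of runs per outcome with four candidates and 9% to 30% with seven. That is about 1.7 to 6 times the nominal 5%. With seven candidates and six outcomes, at least one spurious selection arises in roughly 41% to 74% of runs.

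These figures rest on the assumed 0.05 entry threshold and on assumed correlations among exposures and outcomes. No single value should be quoted without its correlation. The direction is secure: every correlation examined gives more than 5%.

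A reader might go on to infer that the trial's main conclusion is at risk. It is not. The between-group comparison of change scores uses none of these exposure measures, and no decision in the documents rests on this analysis.

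**What to change.** In section 9.2.1, second secondary analysis:

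1. Remove stepwise selection.
2. Name one main exposure in advance, from those already recorded (section 8.1 lists session date, up time, walk time and steps).
3. Pre-specify one linear model in the EAW arm: FIM change on that exposure, with baseline FIM and length of stay as covariates. Length of stay follows from the admission and discharge dates already collected. With three terms and an intercept, 20 participants leave 20 − 4 = 16 residual degrees of freedom.
4. Report every other exposure as a correlation with its 95% confidence interval. Label these hypothesis-generating and state that they will not be used to choose among exposures. Some intervals will exclude zero by chance, so the label matters.
5. Keep logistic regression only if its binary outcome is named in advance; otherwise delete it.

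The cost is a change of wording and fewer exploratory models. No new data, participants or procedures are needed.
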